11.3 Final Analysis Plan

1) (Primary) compare the expression (fold-change relative to baseline) of AIM2 and IFI16 between healthy (PPC-A, PPC-B) and severe periodontitis (PPC-E, PPC-G) subjects during an acute inflammatory response using the stent-induced biofilm overgrowth model

3) (Exploratory) correlate the expression of these proteins with periodontal pathogens

For the primary hypotheses involving gingival tissue samples, univariate and multivariate nonparametric testing procedures for SIBO experiments (Preisser, Sen and Offenbacher, 2011) will be utilized. In particular, a multivariate Wilcoxon Signed Rank test will use all available data to jointly test for changes in AIM2 and IFI16 expression levels over time (visit 2 to visit 5). If the overall multivariate test is statistically significant at the 0.05 level, then univariate Wilcoxon Signed Rank tests will be applied to AIM2 and IFI16 proteins individually. Similar procedures will be applied for expression levels from mRNA and from immunohistochemistry. Additionally, multivariate and univariate Wilcoxon Rank Sum Tests will be applied at the 0.05 significance level to compare SIBO-induced temporal change in Aim2 and IFI16 expression levels between healthy and severe periodontitis subjects.

Parametric statistical procedures will be used to summarize and test periodontal clinical measurements related to secondary hypotheses. Means and their 95% confidence intervals will be used to summarize measurements at each time point in healthy and severe periodontitis subjects. As these measurements will be collected at visits 2, 3, 4 and 5, linear mixed models will be used to assess change over time within groups and differences in change over time between healthy and severe periodontitis groups.

Using 16s rRNA sequencing, expression counts for a large number (~20,000) of Operational Taxonomic Units (OTUs) with known taxonomy will be obtained from 72 samples at baseline and among them approximately 64 samples at Day 21 of SIBO. A few hundred taxa will be identified by collapsing expression data within genera corresponding to candidate periodontal pathogens. Change in pathogen levels from baseline to Day 21 among severe periodontitis subjects will be assessed with univariate Wilcoxon Signed Rank tests applied to each OTU (hypothesis 2f) or Wilcoxon Rank Sum Tests for comparison of Day 21 minus baseline differences in expression counts between healthy and severe periodontitis groups (hypothesis 2h). False discovery rate (FDR; Benjamini and Hochberg, 1995) and family-wise error rate (FWER; Hochberg, 1988) methods, e.g., as described in Preisser et al. (2011), will be applied to resulting *p*-values for exploratory and confirmatory testing, respectively, to identify statistically significant taxa.

Temporal changes in periodontal pathogen levels that are statistically significant controlling for multiple testing as described above will be correlated with stent-induced changes in AIM2 and IFI16 proteins using Spearman rank correlation coefficients and corresponding 95% confidence intervals.

Statistical computation for analysis of the data will be done by [name] in consultation with [name] and [name].

All hypothesis tests that are observed to be NOT statistically significant will be reported as being inconclusive.

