3 OBJECTIVES

3.1 Study Objectives

We will establish 2 new cohorts of individuals: healthy with acute inflammation (SIBO) and chronic periodontitis with acute inflammation (SIBO) to study the role of IFI16 and AIM2 in the pathogenesis of periodontitis. Studying these proteins individually and collectively, along with upstream and downstream events, will yield to new approaches to potentially treat periodontal disease severity and progression. This project will form the basis of a future project involving inflammasomes and alternative therapeutic approaches. The study objectives are to:

1) (Primary) compare the expression of AIM2 and IFI16 between healthy (PPC-A, PPC-B) and severe periodontitis (PPC-E, PPC-G) subjects during an acute inflammatory response using the stent-induced biofilm overgrowth model (SIBO).

2) (Exploratory) correlate the expression of these proteins with periodontal pathogens

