11 STATISTICAL CONSIDERATIONS

11.1 Study Hypotheses

The central hypothesis of this proposal is that IFI16 functions to attenuate the host response that drives periodontitis. We propose to investigate whether macrophage-derived IFI16 expression modulates tissue inflammation via AIM2. Human tissues will be used for confirming results generated by the principal investigator from in vitro and in vivo models that show high expression of AIM2 and IFI16 under inflammatory conditions (4). Better characterization of the cellular and molecular biology of inflammasomes will help identify important potential therapeutic targets for the treatment and prevention of periodontal diseases. The following “hypothesis” corresponding to Study Objective 1 (section 3.1) is:

Primary hypotheses corresponding to the second study objective **will be tested**:

- 1a. There will be a temporal change in expression of AIM2 (mRNA fold change and percentage of positive cells for histological analysis) induced by SIBO in healthy and severe periodontitis subjects
- 1b. There will be a temporal change in expression of IFI16 (mRNA fold change and percentage of cells for histological analysis) induced by SIBO in healthy and severe periodontitis subjects
- 1c. There will be differences in temporal changes in expression of AIM2 (mRNA fold change and percentage of cells for histological analysis) induced by SIBO between healthy and severe periodontitis subjects
- 1d. There will be differences in temporal changes in expression of IFI16 (mRNA fold change and percentage of cells for histological analysis) induced by SIBO between healthy and severe periodontitis subjects

Exploratory hypotheses corresponding to the second study objective will be assessed:

- 2a. The stent-induced change in expression of protein AIM2 will correlate with differentially expressed (between healthy and severe periodontitis subjects) periodontal pathogens identified by 16S rDNA (% of total reads) at baseline (visit 2)
- 2b. The stent-induced change in expression of protein IFI16 will correlate with differentially expressed (between healthy and severe periodontitis subjects) periodontal pathogens identified by 16S rDNA (% of total reads) at baseline (visit 2)
- 2c. The stent-induced change in expression of protein AIM2 will correlate with the temporal change in periodontal pathogens identified by 16S rDNA (% of total reads)

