11.2 Sample Size Considerations

In order to evaluate the expression of IFI16 and AIM2 in subjects, 72 (36 subjects/group) will be recruited from the patients, students, staff and general population at the University of North Carolina-School of Dentistry. We will enroll 72 subjects to accommodate a 10% drop-out rate. Individuals with healthy tissues and severe periodontitis will be enrolled based on Morelli et al 2017 (1). Sample size calculations are based, in part, on preliminary cross-sectional (non-SIBO experiment) data on expression levels of Aim2 from immunohistochemistry reported in Xue et al. (2015; Table 3) who reported statistically significant differences in healthy (n=10; mean=0.50; s.d.=0.14) and severe periodontitis (n=10; 0.97; s.d.=0.27) subjects with respect to AIM2 expression from immunohistochemical analyses. For the first study objective (section 3.1), there will be 99% power to detect differences in AIM2 and IFI16 expressions at Visit 2 between healthy and severe periodontitis at these levels using two-sided t-tests at the 0.05 significance level. When comparing change in AIM2 expression levels from visit 2 to visit 5, assumptions of a common standard deviation of 0.25 and an intra-subject correlation of 0.40 across the two time points indicate that power will be at least 80% to determine differences in change between healthy and severe periodontitis subjects that are as small as 0.40; in a worst case (but not realistic) scenario, an intra-subject correlation of 0 would give 80% power to detect differences in temporal change that are as small as 0.50. Xue et al (2015; Figure 1c) found no statistically significant cross-sectional differences between healthy and severe periodontitis subjects with respect to mRNA expression of AIM2; they did not report this data numerically precluding power analysis.

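### Section 11.3 repeats 0.05-level tests of primary hypotheses 1a–1d over two assays and two comparisons without sharing alpha, and states no condition for the univariate rank-sum tests

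*Combined protocol and SAP*

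**What the plan says.** Section 11.1 labels 1a–1d as primary. Hypotheses 1a and 1b concern change over time in AIM2 and IFI16; 1c and 1d concern the difference in that change between healthy and severe subjects. Each names both assays, for example "There will be a temporal change in expression of AIM2 (mRNA fold change and percentage of positive cells for histological analysis".

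Section 11.3 starts with a multivariate signed-rank test that "will use all available data to jointly test for changes in AIM2 and IFI16 expression levels over time". The follow-up is conditional: "If the overall multivariate test is statistically significant at the 0.05 level, then univariate Wilcoxon Signed Rank tests will be applied". The procedure is repeated by assay: "Similar procedures will be applied for expression levels from mRNA and from immunohistochemistry". For the group comparison, the text says only that "multivariate and univariate Wilcoxon Rank Sum Tests will be applied at the 0.05 significance level to compare SIBO-induced temporal change".

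The false discovery rate and Hochberg methods later in section 11.3 are there to identify taxa. Its closing line has non-significant tests reported as inconclusive.

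The primary family is described in more than one way. Section 3.1 gives the primary objective as "Primary) compare the expression of AIM2 and IFI16 between healthy (PPC-A, PPC-B) and severe periodontitis (PPC-E, PPC-G) subjects", which is a between-group comparison, and section 11.3 opens with the same objective. Section 11.1 also makes within-group change primary, and introduces the list as "Primary hypotheses corresponding to the second study objective", although section 3.1 calls the second objective exploratory.

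**The concern.** Four points are left open: whether the univariate rank-sum tests need a significant joint test, whether the signed-rank test is pooled or run by group, which comparisons are primary, and what counts as success when the two assays disagree. The last is foreseeable. Section 11.2 reports that the earlier study found an AIM2 difference by IHC but no significant one in mRNA.

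Reporting negatives as inconclusive sets no rule for a single positive among several tests. Section 11.1 says that the human tissue is meant to confirm results from laboratory models, so a lone significant result could be read as that confirmation. The plan also provides family-wise control for taxa, under an objective labelled exploratory, but none across the primary AIM2 and IFI16 tests.

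**Working it through.** **Inputs.** Section 11.2: 36 per group, 10% dropout, SD 0.25, intra-subject correlation 0.40 (worst case 0), two-sided 0.05. Evaluable subjects: 36 × 0.9 = 32.4, taken as 32 per group. This agrees with 128 biopsies at two per subject (section 7.3.1), or 64 subjects. The correlations between the two proteins (0 to 0.8) and between the two assays (0 to 0.9) are assumptions, because the documents give neither.

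**The plan's own figure.** SD of change = 0.25 × √(2 × (1 − 0.40)) = 0.274; at correlation 0 it is 0.25 × √2 = 0.354. Section 11.2 states at least 80% power for "differences in change between healthy and severe periodontitis subjects that are as small as 0.40". A noncentral-t calculation with 32 per group gives 99.99% power at 0.40 and an 80%-power difference of 0.195 (0.252 at correlation 0). The stated figure is true but loose, which leaves room for a stricter level.

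**One assay, one comparison.** The joint test at 0.05 covers the null for both proteins together, and each univariate test at 0.05 covers one protein. Claiming a protein only when both tests reject is a closed test, so the error rate is at most 0.05. With AIM2 truly changing, the simulated false IFI16 rate was 4.7–5.3% per comparison in IHC. The conditional step works as intended.

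**Repetition.** If the joint tests were independent, the chance of at least one false rejection would be:
- two tests (between-group, two assays): 1 − 0.95² = 9.75%
- four tests (signed-rank pooled): 1 − 0.95⁴ = 18.5%
- six tests (signed-rank by group): 1 − 0.95⁶ = 26.5%

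**Simulation.** 20,000 trials per setting, 32 per group, bivariate rank tests referred to chi-square on 2 df, then univariate rank tests. The table gives the chance of at least one false AIM2 or IFI16 claim in either assay.

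| Counted as primary | Rank-sum follow-up conditional | Unconditional, as written |
|---|---|---|
| Between-group tests only, no true difference | 5.2–8.7% | 11.5–18.7% |
| All of 1a–1d, global null, signed-rank pooled | 9.9–16.7% | 15.9–25.7% |
| All of 1a–1d, global null, signed-rank by group | 11.7–19.9% | 16.4–27.0% |

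With both correlations at 0.9, the first two rows fall to 4.6% and 10.1%, and to 9.0% and 14.3%.

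**AIM2 changes, IFI16 does not.** Take an AIM2 change of 0 in healthy and 0.40 in severe subjects (the size is from section 11.2; its placement is assumed). A false IFI16 claim then occurs in:
- 13–19% of trials if AIM2 changes in both assays, conditional or not
- 11–15% if AIM2 changes in IHC only and the follow-ups are conditional
- 7–10% if only the between-group tests count and AIM2 changes in both assays

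**After sharing alpha.** Four joint tests at 0.05/4 = 0.0125 have a total of at most 4 × 0.0125 = 0.05. Simulated false claims are 2–5% under the global null, and false IFI16 claims are 3–5%. If the joint tests run at 0.0125 but the follow-ups stay at 0.05, false IFI16 claims remain at 13–19%.

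**The case against.** This is a mechanistic study with four separately stated hypotheses, and nothing in it promises a 5% rate over all of them. That stands. A reader might infer a promise from section 5.5, which mentions strong control of the error rate. That text names no procedure and refers to 200 participants and four groups, which is not this study. It supports no claim that a stated guarantee is breached.

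The rank-sum condition may be intended, since the procedures come from a cited methods paper and are called similar across assays. That is possible, and the conditional column then applies.

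The primary objective in sections 3.1 and 11.3 is between-group, and so is every power figure in section 11.2. The plan also expects high AIM2 and IFI16 expression under inflammation. If both proteins do change over time, only the between-group nulls remain, and 5–9% (conditional) or 12–19% (unconditional) is the relevant figure. A reader might take 16–27% as the trial's error rate. It requires the unconditional reading, all of 1a–1d as primary, and no effect of any kind.

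A reader might also conclude that a real AIM2 change exposes IFI16 through the joint test. It does not: the error stays at 0.05 within one assay and one comparison. The excess comes from repeating the procedure. The 13–19% figure also assumes an equal AIM2 effect in both assays. Section 11.2's cross-sectional mRNA evidence fits the IHC-only case (11–15%) better.

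**Conclusion.** The point holds as a cheap improvement. The plan writes no condition for the univariate rank-sum tests, shares no alpha across assays or comparisons, and does not settle which comparisons are primary. The false-claim rate runs from 5–9% on the narrowest reading to 16–27% on the widest. Where AIM2 changes and IFI16 does not, with all of 1a–1d counted, false IFI16 claims occur in about 11–19% of trials. The narrowest reading is a modest excess, but the documents do not say that it is the one meant.

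The figures rest on 32 per group, the plan's AIM2 IHC standard deviation and the assumed correlations. They cover 1a–1d only. Section 3.2 also lists clinical measurements and microbiota as primary outcomes, and section 11.2 powers a Visit 2 comparison under the first objective. A reader should not take the 0.05 bound in the fix to include these.

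**What to change.** In section 11.3, with matching wording in sections 3.1 and 11.1:

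1. Run the univariate rank-sum tests only if the joint rank-sum test for that assay is significant, as is already done for signed-rank.
2. State whether the joint signed-rank test is pooled or by group, and make the three sections agree on which comparisons are primary.
3. Share alpha across the primary joint tests and run each follow-up at the same level as its joint test. Use 0.05/4 for all of 1a–1d with pooled signed-rank, or 0.05/6 if by group (2–4% false claims). Use 0.05/2 if only the between-group tests in both assays are primary, or if IHC is named primary and mRNA secondary (signed-rank pooled). A Hochberg-type step-up, which the plan already names for taxa, is an alternative if its dependence conditions are acceptable; its follow-up levels would need to be written out, and it was not simulated here.
4. State that the section 3.2 clinical and microbiota outcomes and the Visit 2 comparison lie outside this family.

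**Cost.** SAP wording and some precision, with no added subjects. At 0.05/4 the 80%-power between-group difference (t-test) rises from 0.195 to 0.235, and power for 0.40 is 99.9% (97% at correlation 0). The pooled signed-rank detectable change rises from 0.10–0.11 to 0.12–0.135. Pooling does not show which group changed. By group at 0.05/6 the between-group figure is 0.245, and the within-group detectable change is 0.19–0.21. At 0.05/2 the between-group figure is 0.216. These costs use the AIM2 IHC standard deviation for both proteins. The mRNA cost cannot be calculated, because section 11.2 had no numerical mRNA data.

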3.2 Study Outcome Measures

Primary study outcomes measured for individuals in each group (healthy and severe periodontitis):

- Expression of AIM2 and IFI16 levels will be quantified by IHC and qRT-PCR
- Periodontal clinical measurements
- Composition of oral microbiota by 16S rDNA (Illumina)

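### Section 11.3 tests within-person microbial change only in the severe group: the healthy cohort gets no within-group test, and shifts shared by both groups are tested on about 32 of about 64 pairs

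*Combined protocol and SAP*

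**What the plan says.** Section 11.3 names two tests of microbial change. The first is within person: "Change in pathogen levels from baseline to Day 21 among severe periodontitis subjects will be assessed with univariate Wilcoxon Signed Rank tests", applied per OTU and labelled hypothesis 2f. The second is between groups: "Wilcoxon Rank Sum Tests for comparison of Day 21 minus baseline differences in expression counts between healthy and severe periodontitis groups (hypothesis 2h"). Taxa whose temporal change survives the multiplicity correction are then correlated, by Spearman coefficients, with the stent-induced changes in AIM2 and IFI16.

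Other parts of the document draw no such group limit:

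- Section 3.1 sets up two SIBO cohorts, one healthy and one with chronic periodontitis. Section 4 has plaque taken from all participants at baseline and at 21 days.
- Section 3.2 lists microbiota composition under "Primary study outcomes measured for individuals in each group (healthy and severe periodontitis").
- Hypothesis 2c in section 11.1 reads "The stent-induced change in expression of protein AIM2 will correlate with the temporal change in periodontal pathogens identified by 16S rDNA", with no restriction to severe disease. Hypothesis 2d says the same for IFI16.
- For the tissue markers, section 11.3 runs the signed-rank test on every participant with data. For the clinical measurements it assesses change within each group.

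Section 11.1 stops at hypothesis 2d. The labels 2f and 2h in section 11.3 refer to nothing in the document.

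**The concern.** SIBO is applied to everyone, so taxa that move in both groups are a natural thing to look for. Under the plan as written, such a taxon can be found only through the severe-group test, which uses half of the available pairs. The rank-sum test compares the change in one group with the change in the other. When the two shifts are equal, it has nothing to detect. A taxon that moves only in healthy participants has no direct test; it can show up only as a between-group difference, which is a weaker route.

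The consequence goes beyond a missing line in a table. Significant temporal change is the entry condition for the 2c and 2d correlations. A taxon missed here is not correlated with AIM2 or IFI16 at all, although those hypotheses are not confined to severe disease.

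**Working it through.** **Pairs.** Section 11.2 states "72 (36 subjects/group) will be recruited" and "We will enroll 72 subjects to accommodate a 10% drop-out rate". Then 72 × 0.90 = 64.8 and 36 × 0.90 = 32.4. This reproduces the figure in section 11.3, "72 samples at baseline and among them approximately 64 samples at Day 21 of SIBO", or about 32 pairs per group. The severe-only test therefore uses about 32 of about 64 pairs.

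**Assumptions.** The document gives no SD or effect size for any taxon, so effects are in SD units of within-person change, taken as normal. On the number of tests, section 11.3 says "A few hundred taxa will be identified by collapsing expression data within genera corresponding to candidate periodontal pathogens". I use 300, with a range of 100 to 500. The cut-off 0.05/300 stands for strict family-wise control, and 0.005 for a typical false-discovery-rate cut-off.

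**What each test can see.** Write δs and δh for the mean changes in the severe and healthy groups. The approximate signal, using the rank-test efficiency 0.955, is:

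- signed-rank on n pairs with shift δ: δ × √(0.955 n)
- rank-sum with n per group: (δh − δs) × √(0.955 n/2)

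For a shared shift of 0.6 SD:

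- severe only: 0.6 × √(0.955 × 32) = 3.32
- all pairs: 0.6 × √(0.955 × 64) = 4.69
- rank-sum: (0.6 − 0.6) × √(0.955 × 16) = 0

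For a healthy-only shift of 0.8 SD:

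- signed-rank in the healthy group: 0.8 × √(0.955 × 32) = 4.42
- rank-sum: 0.8 × √(0.955 × 16) = 3.13

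The two-sided critical value at 0.05/300 is 3.765. Turning these signals into power with the normal curve is too generous at cut-offs this small with 32 pairs. It gives Φ(3.32 − 3.765) = 33%, against 21% by simulation. The figures below are therefore simulated, with exact signed-rank and asymptotic rank-sum p-values and 32 per group.

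| Shared shift of 0.6 SD, cut-off | Severe only, 32 pairs | All, 64 pairs |
|---|---|---|
| 0.005 | 62% | 96% |
| 0.05/100 | 32% | 85% |
| 0.05/300 | 21% | 76% |
| 0.05/500 | 18% | 71% |

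The 64-pair column is one signed-rank test on all pairs, taken as a close stand-in for the group-stratified form. On the same equal shifts, the rank-sum test rejects 4.8% of the time at 0.05, which is its null rate.

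**Healthy-only shift of 0.8 SD at 0.05/300.** A signed-rank test in the healthy group has about 57% power. The planned rank-sum test has about 17%.

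**Cost of extra tests.** Three signed-rank tests per taxon (all, healthy, severe) make 3 × 300 = 900. At 0.05/900, 64 pairs still give about 66% for the shared shift, against 21% now: a gain of 45 points. The healthy-only test gives about 44% against 17%: a gain of 27 points. By symmetry, a severe-only shift of 0.8 SD falls from about 57% to about 44%, a loss of 13 points under this strict rule.

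**The case against.** The strongest reply is that no listed hypothesis asks whether the healthy microbiome changes. Hypotheses 2a to 2d are all correlations, whereas 1a and 1b name temporal change in both groups outright. Section 3.1 labels the pathogen objective exploratory, and the AIM2 and IFI16 tests are untouched. Taxa may also qualify through the rank-sum route. All of this stands, and it limits the weight of the point. It does not defend the restriction: no listed hypothesis calls for a severe-only test either, and the rank-sum route is closed to shared shifts.

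A particular interest in diseased sites would be a fair reason for a severe-group test. The document does not state one, and it would not explain leaving out the other group.

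Three stronger readings are tempting but not supported:

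- **The healthy microbial response goes unreported.** Section 3.2 lists composition in each group, and section 7.3.1 evaluates diversity and relative abundance with no group limit. What is missing is a within-group test.
- **Microbial change is tested only in severe participants.** This is true of within-person change only, because healthy changes enter the rank-sum test.
- **A healthy or pooled test was dropped from a longer hypothesis list.** The stray labels 2f and 2h might suggest it, but the document does not show what was intended.

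**Conclusion.** The point holds for within-person testing. As written, section 11.3 leaves the healthy SIBO cohort without a within-group test of microbial change and tests shared shifts on half the pairs. At a shared 0.6 SD, this costs about 34 points of power at p=0.005 (96 − 62) and about 55 points at 0.05/300 (76 − 21). The levels depend on assumed effect sizes, normal changes, the number of taxa and the cut-off. The direction does not: half the pairs always carry less information on a shared shift, and the rank-sum test carries none.

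The step is exploratory, so this should be corrected before analysis but does not threaten the primary results. Its practical consequence is a shorter and differently chosen list of taxa for the 2c and 2d correlations.

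**What to change.** In section 11.3:

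1. Remove the restriction to the severe group. Specify a signed-rank test on all approximately 64 pairs, stratified by group, as the test that selects taxa for the 2c and 2d correlations.
2. Add signed-rank tests within the healthy and the severe group, and keep the rank-sum comparison.
3. Place all of these in the false-discovery-rate and family-wise families that section 11.3 already names.
4. Reconcile labels 2f and 2h with section 11.1, either by adding the missing hypotheses or by relabelling the tests.

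No new samples or visits are needed; this is a change of SAP wording. There are two costs. The testing family grows, so the severe-group test loses some power. A shift confined to one group is also diluted in the pooled test: 0.8 SD in one of two equal groups averages 0.8/2 = 0.4 SD overall. The plan should therefore say whether a taxon that is significant only within one group, or only in the rank-sum test, also goes on to the correlations.

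### Section 11.3 plans no analysis for exploratory hypotheses 2a and 2b, words one taxon test on counts rather than % of total reads, and leaves the grouping of the Spearman correlations unstated

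*Combined protocol and SAP*

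**What the plan says.** Section 11.1 gives four exploratory hypotheses. In 2a (AIM2) and 2b (IFI16), the stent-induced protein change is related to pathogens that differ between the healthy and severe groups at visit 2. In 2c and 2d it is related to the change in pathogens over time. All four express pathogens as % of total reads, and section 7.3.1 names the same scale for the 16S results.

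Section 11.3 says sequencing counts "will be obtained from 72 samples at baseline and among them approximately 64 samples at Day 21 of SIBO", and that "A few hundred taxa will be identified by collapsing expression data within genera". It then plans:

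- a within-group test: "Change in pathogen levels from baseline to Day 21 among severe periodontitis subjects will be assessed with univariate Wilcoxon Signed Rank tests", run per OTU and labelled hypothesis 2f;
- joined by *or*, a Wilcoxon rank-sum comparison of "Day 21 minus baseline differences in expression counts between healthy and severe periodontitis groups (hypothesis 2h";
- FDR control for exploratory and FWER control for confirmatory testing;
- a correlation step: "Temporal changes in periodontal pathogen levels that are statistically significant controlling for multiple testing as described above will be correlated with" the AIM2 and IFI16 changes, by Spearman coefficients with 95% CIs.

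The exploratory objective is numbered "3) (Exploratory) correlate the expression of these proteins with periodontal pathogens" in 11.3 but "2) (Exploratory) correlate the expression of these proteins with periodontal pathogens" in 3.1.

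**The concern.** An analysis section should carry a method for each listed hypothesis, on the scale in which that hypothesis is stated. Here two of the four have none, so any analysis of 2a or 2b would be devised after the data are in hand. For 2c and 2d, taxa could be screened on a scale that depends on sequencing depth. A reported correlation could also reflect the difference between disease groups, an association within groups, or both, and a reader could not tell which.

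**Working it through.** **Plan's own figure.** With 10% dropout, 72 × 0.90 = 64.8; per group 36 × 0.90 = 32.4, so 32 per group and 64 in all. This agrees with the approximately 64 Day 21 samples in 11.3.

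**1. Hypotheses against planned analyses**

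| Hypothesis | Pathogen variable | What it needs | What 11.3 has |
|---|---|---|---|
| 2a, 2b | Baseline level of taxa that differ between groups | Baseline between-group test, then correlation with baseline level | Neither |
| 2c, 2d | Change in % of total reads | Correlation with change | Present for significant changes; scale and grouping open |
| 2f, 2h | Not listed in 11.1 | – | Labels attached to the two change tests |

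A taxon that differs at baseline reaches the Spearman step only if it also shows a significant change. Even then its change is correlated, not its baseline level. No simulation is needed for this part.

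**2. Scale.** For a taxon whose true share p does not change, the expected count difference is p × (depth at Day 21 − depth at baseline). For instance, take 20,000 reads at baseline and a depth ratio of 1.2. A 2% taxon gains 0.02 × 20,000 × 0.2 = 80 reads and an 8% taxon gains 320, although neither share has changed. The two groups' count differences are therefore comparable only if depth shift and abundance are the same in both.

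Illustration with assumed inputs, as the documents give no depth or abundance figures: 32 per group, median share 2%, log SD 0.8 between and 0.4 within persons, median depth 20,000, library log SD 0.4, binomial counts, 5,000 replicates. Rank-sum rejection of a null taxon at the 5% level:

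| Depth ratio | Equal shift and abundance | Four-fold abundance in severe | Shift in severe only |
|---|---|---|---|
| 1.2 | 5.3% | 11.7% | 12.4% |
| 1.3 | 4.9% | 17.0% | 21.1% |
| 1.5 | 5.3% | 31.4% | 45.6% (48% in a repeat run) |

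On % of reads the rate is 4.4–6.5%.

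**3. Grouping of the Spearman coefficient.** From 11.2, with SD 0.25 and intra-subject correlation 0.40, the SD of change is 0.25 × √(2 × (1 − 0.40)) = 0.274. With 32 per group, the difference detectable with 80% power is (1.96 + 0.842) × 0.274 × √(2/32) = 0.192 by the normal approximation (about 0.195 by t). I therefore take a protein difference of 0.20, which is 0.20/0.274 = 0.73 SD.

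Further assumptions: 300 taxa (for a few hundred), 30 of them with a change that differs between groups, independent normal variables, zero association within groups, rank-sum screen under Benjamini–Hochberg at 5%, 3,000 replicates. Spearman CIs use Fisher z with variance 1.06/(n − 3).

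| Taxon difference in change | Pass screen | Pooled CI excludes 0, given pass | Pass and exclude 0 (product) |
|---|---|---|---|
| 0.5 SD | 3.8% | 24.5% | 0.9% |
| 1.0 SD | 81.1% | 24.3% | 19.7% |
| 1.5 SD | 99.8% | 36.8% | 36.7% |

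A repeat run gave 27%, 26% and 36% in the third column. The stratified CI excludes zero in 4–5% of passing taxa. With no protein difference the pooled figure is about 4%.

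**4. Price of stratifying.** The CI half-width near zero is tanh(1.96 × √(1.06/df)). Pooled (df 61) it is 0.253, stratified (df 29 + 29 = 58) 0.259, one group (df 29) 0.358.

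**The case against.** The objective is labelled exploratory throughout, and no sample, assay or primary test depends on it. That limits the weight of the point but does not supply a method for 2a and 2b.

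On scale, a reader might infer that raw counts will be analysed. The documents do not establish this. Section 7.3.1 plans relative abundance, all four hypotheses use it, and 11.3 itself speaks of pathogen levels in the signed-rank sentence. The rank-sum wording may simply reuse the noun for what sequencing yields. What stands is a conflict of wording; the inflated rates follow only if it is read literally and depth or abundance differs by group.

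On grouping, a reader might call a pooled correlation a false positive. It is not: the marginal association is real, and 11.1 does not say which association is meant. The calculation also covers only the rank-sum screen. Taxa entering through the signed-rank test in severe subjects were not selected on a group difference, so these percentages do not describe them.

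A larger effect could be shown with the 0.40 difference named in 11.2 (65%, 66% and 87% in place of the third column). That is a poor basis. Under the plan's inputs, power at 0.40 with 32 per group is 99.99%, about twice the difference detectable with 80% power.

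The stray labels and objective number are clerical on their own, since 11.3 describes each test in words. They do not show which section is out of date.

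**Conclusion.** The point holds. That 2a and 2b have no planned analysis follows from the text alone. The scale conflict is also plain on the page, but its consequence is conditional: about 12–48% rejection of a null taxon at depth ratios 1.2–1.5 under literal counts with unequal shift or abundance, about 5% if both are equal, and about 5% on % of reads. The unstated grouping is a gap in interpretation: with a protein difference of 0.20, roughly 25–37% of taxa passing the rank-sum screen under FDR would show a pooled interval excluding zero without any within-group association. Taxon effects, number of taxa, depth and abundance are all assumed. Primary hypotheses 1a–1d are not affected.

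**What to change.** In 11.1 and 11.3:

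- **(a)** State that all taxon tests and correlations use % of total reads.
- **(b)** For 2a/2b, add a baseline rank-sum test between healthy and severe at the collapsed-taxon level, with FDR control (11.3's own rule for exploratory testing). Then correlate the selected taxa's baseline % of reads with the AIM2 and IFI16 change.
- **(c)** Make the group-stratified Spearman coefficient the main estimate: the inverse-variance average of the two within-group Fisher z values, back-transformed, with its 95% CI. Show the within-group values descriptively, and label any pooled value as a marginal association that includes the group difference.
- **(d)** As clean-up, replace 2f/2h and the objective number with labels that match 11.1. State which screen or screens select taxa for 2c/2d, resolving the *or* and the restriction of the signed-rank test to severe subjects. State whether tests are run per OTU or per genus.

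The cost is wording, one more multiplicity-controlled family of tests, and a CI half-width of 0.26 rather than 0.25. At a true Spearman correlation of 0.3, power is about 63% stratified against 65% pooled. It is about 37% in one group, which is why the within-group values should be descriptive. No new samples or assays are needed.
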